system, skin, musculoskeletal system, height (screening only), weight, pulse, blood pressure, monitoring for volume depletion, and assessment for ketoacidosis (difficulty breathing, nausea, vomiting, abdominal pain, confusion, and unusual fatigue or sleepiness).

- b) Screening laboratory assessment includes HbA1c, BNP, NTproBNP and renal panel.
- c) Randomization, Week 6 and Week 12 laboratory assessment includes HbA1c, Fasting Glucose, BNP, NTproBNP, CBC, renal panel, and collection of samples for future potential biomarker analyses (Randomization and Week 12 only).
- d) Week 13 laboratory assessment includes only renal panel.
- e) Only for women with childbearing potential.
- f) Phone visits include recording any AE or SAE, self-monitoring of weight and blood glucose (patients with established type 2 diabetes only), and encouraging compliance with study medication.
- g) Visit Windows: There may be up to 2 weeks between the screening and randomization visits. Week 6, 12 and 13 clinic visits have a +/- 2-day visit window. Phone Visits have a +/- 2-day visit window.
- h) An echocardiogram will be completed in those subjects participating in echo sub study at Visit 1 (Week 0 Randomization) and Visit 7 (Week 12)
- i) The urine specimens collected at 0, 6 and 12 weeks will only be checking urine albumin and urine creatinine. It will not be a standard urinalysis, and any clinical suspicion of urinary tract infection will be left to the local investigator or patient's primary care physician to order a proper screening test to evaluate.
- j) If a patient is a screen failure at the initial screening visit, they may be rescreened on three additional occasions at the discretion of the investigator. At the rescreening visit, the patient should be treated like a new patient and assigned a new subject number and all screening visit procedures should be completed, including obtaining informed consent.
- k) Subjects should be resting in the supine position for at least 5 minutes prior to collection of blood samples for biomarkers at Visit 1 (Week 0 Randomization) and Visit 7 (Week 12).
- l) For all patients, their most recent clinically available echocardiogram prior to study enrollment will be submitted using the WebPAX system, if feasible. This will be a historical Echo which is a part of the patient record and is independent to any study-related Echo image acquisition.

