1.3 Sample Size and Power

Planned Sample Size	Approximately 160 patients will be enrolled in each arm.
Power Statement	For the primary endpoint a sample size of 145 for each group will achieve 82% power with $\alpha=0.05$ to detect a 4.7 difference in mean KCCQ CS between dapagliflozin group and placebo group at 12 weeks. The assumptions for this calculation was derived from DEFINE-HF trial where the adjusted mean difference between dapagliflozin group and placebo group is 4.7 and the standard deviation is 13.7. Assuming a 10% loss to follow up, we arrive at a sample size of ~320 patients.

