2.5 Multiple Testing

The primary endpoint will be tested at the 2-sided 5% significance level. No adjustments for multiplicity will be made for secondary and exploratory endpoints.

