2.6 Missing Data

There are three possible sources for missing data:

1. Deaths
2. Administrative error
3. Premature study terminations

Missing data due to deaths is expected to be very low (fewer than 10 patients) because of the short follow-up period. Missing data due to administrative error is believed to be negligible due to the study management procedures and is also believed to be missing completely at random (MCAR). For patients who drop out of the study prematurely, a premature treatment discontinuation visit (PTDV) will be scheduled for them, whenever possible, to get the last assessment. The PTDV assessment will be carried forward to the next follow-up time point. For partially completed KCCQ questionnaires, the scoring algorithm accommodates a limited number of skipped responses. Values that are missing at randomization but available at screening will be imputed using the value at screening. Primary, secondary, and exploratory endpoints will be analyzed among patients for whom all relevant data for the given endpoint can be calculated.

For KCCQ scores, additional sensitivity analysis will be conducted using multiple imputation to account for missing values. IVEware (Raghunathan et al. 2002) will be used to perform the multiple imputation which employs iterative sequential regression to sample missing values from the predictive distribution of each variable, conditional on all other variables included in the imputation model. The following variables will be included in the imputation model: baseline KCCQ scores, sex, baseline eGFR, history of diabetes (DM), history of permanent AFib, baseline LVEF, baseline NYHA class, heart failure hospitalization during the trial duration, urgent heart failure visit during the trial duration, and covariates used as subgroup variables in section 2.3. Additionally, the imputation model will also include all follow up

assessments available for KCCQ scores, eGFR, NTproBNP, BNP, Hgb, loop Diuretic dose, 6-minute walk test.

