3.3	Admission for an acute coronary syndrome (ST-elevation MI, non-ST-elevation MI, or unstable angina), percutaneous coronary intervention, or cardiac surgery during the study period.	Other	To be decided on a case by case basis
4. Patient received prohibited concomitant medication but study treatment not discontinued:			
4.4.1	SGLT2 inhibitors	Other	Only the efficacy endpoints before the start of prohibited medication will be included in PPS analysis
5. Patient received incorrect investigational treatment/dose			
5.0	Patient took incorrect treatment or damaged Investigational Drug Kit	MIA	To be decided on a case by case basis
5.1	Major compliance issues <80% or >120% compliance with IP dosing in double blind treatment period	MIA	To be decided on a case by case basis
5.2	Patient randomized but never took IP	MIA	To be decided on a case by case basis

5.3	Overdose	MIA	To be decided on the case by case basis
6. Protocol-required procedure not adhered to:			
6.0	Study data collection has not been stopped when subject decided to withdraw their consent from the study completely	Other	No exclusion from PPS Data collected after consent withdrawal to be excluded from data base
6.1	Patients with absence of NT-proBNP data at randomization visit and having values at Screening visit.	Other	No exclusion from PPS Values from screening visit will be used to impute the values at randomization visit.
6.2	Patients with absence of baseline NT-proBNP data at both screening and randomization visits	Other	Excluded from the NT-proBNP analyses
6.3	Patients with no NT-proBNP values after randomization	Other	Excluded from the NT-proBNP analyses
6.4	Patients with absence of baseline KCCQ clinical summary score at randomization visit	Other	Excluded from the ITTS KCCQ analyses
6.5	Patients with no KCCQ clinical summary score after randomization	Other	Excluded from ITTS KCCQ analyses
6.6	Patients with absence of baseline 6-minute walk assessment at randomization visit	Other	Excluded from the 6-minute walk analyses
6.7	Patients with no 6-minute walk assessment after randomization	Other	Excluded from 6-minute walk analyses
6.8	Patients with missing values in the covariates: gender, Hx AFib, AFib type, Hx DM, eGFR at randomization, lvef at randomization	Other	No exclusion from PPS Excluded from the first and second primary analysis

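### SAP 10.2 item 6.8 removes patients with an observed outcome from the primary ANCOVA when a baseline covariate is missing, and for eGFR it does not carry over the screening-value rule

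*SAP*

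**What the plan says.** SAP 6.1 plans an ANCOVA of the 12-week KCCQ clinical summary score, adjusted for its baseline value, sex, eGFR, diabetes status, permanent atrial fibrillation and LVEF.

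SAP 10.2 item 6.8 deals with "Patients with missing values in the covariates: gender, Hx AFib, AFib type, Hx DM, eGFR at randomization, lvef at randomization". Its stated consequence is no exclusion from the per-protocol set, but exclusion from a first and a second primary analysis. SAP 4.1 lists only one primary endpoint.

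SAP 2.6 gives a general rule: "Values that are missing at randomization but available at screening will be imputed using the value at screening". Item 6.1 of the deviations table repeats this rule for NT-proBNP. Item 6.8 does not mention it.

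SAP 2.7 says that eGFR is not calculated when creatinine, age, race or sex is missing.

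On LVEF, Protocol Table 1 footnote h says "An echocardiogram will be completed in those subjects participating in echo sub study at Visit 1 (Week 0 Randomization", with a second echocardiogram at Week 12. No other patient has a study echocardiogram at randomisation. Protocol 4.1 nevertheless requires a qualifying ejection fraction from imaging within 24 months for every patient, and SAP 5.2.2 lists the most recent LVEF assessment among the baseline characteristics.

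**The concern.** The modified ITT definition in SAP 2.1 ties exclusion from an endpoint to the absence of follow-up data for that outcome. Item 6.8 adds a second condition: a patient who was randomised, treated and followed, and who completed the 12-week questionnaire, leaves the primary analysis because an adjustment variable is blank.

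This is a poor trade. Covariates are in the model to gain precision. In a randomised trial a baseline covariate is independent of arm, so filling a gap by a rule that looks at neither arm nor outcome does not bias the treatment effect. Dropping the patient discards an observed outcome.

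The item is also hard to carry out as written. For a patient with a screening eGFR but no randomisation eGFR, 2.6 keeps the patient and the wording of 6.8 removes the patient. The LVEF entry names a visit at which most patients have no scheduled measurement. *AFib type* is not itself a model term. The row keeps such patients in the per-protocol set, yet SAP 6.1 analyses that set with the same model, which needs the same covariates.

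**Working it through.** **Which covariates are affected**

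| Item 6.8 covariate | Where a value exists | Does the 2.6 screening rule help? |
|---|---|---|
| Sex | Enters the eligibility eGFR formula (Protocol 4.2, criterion 4) | No separate randomisation value |
| AF history and type | Permanent AF is a randomisation stratum (Protocol 4 and 12.2) | No separate randomisation value |
| Diabetes history | Randomisation stratum | No separate randomisation value |
| eGFR | Renal panel at screening and at randomisation (Protocol Table 1 footnotes b and c; Table 3) | Yes, but 6.8 names randomisation and does not invoke the rule |
| LVEF | Qualifying imaging within 24 months for all; randomisation echocardiogram in the substudy only | A value known before randomisation exists for every eligible patient |

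The conflict with 2.6 is therefore specific to eGFR, the only listed covariate with a scheduled measurement at both visits. A missing race is a separate route to loss: under 2.7 it blocks the calculation at either visit, so the screening rule would not rescue that patient.

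**Reproducing the plan's power**

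Inputs from SAP 1.3 and 2.5:
- "For the primary endpoint a sample size of 145 for each group will achieve 82% power"
- "the adjusted mean difference between dapagliflozin group and placebo group is 4.7 and the standard deviation is 13.7"
- "The primary endpoint will be tested at the 2-sided 5% significance level"
- "Approximately 160 patients will be enrolled in each arm"
- "Assuming a 10% loss to follow up, we arrive at a sample size of ~320 patients"

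Power = Φ( δ / (σ√(2/n)) − 1.96 ), with δ = 4.7, σ = 13.7 and n per arm.

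At n = 145: σ√(2/145) = 1.609; 4.7/1.609 = 2.921; 2.921 − 1.96 = 0.961; Φ(0.961) = 83.2%. The noncentral t version gives 82.9%. Both agree with the stated 82% to within about one point.

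For loss to follow-up, 290/0.9 = 322.2, rounded up to 323, and 290 × 1.1 = 319. Both agree with about 320.

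**Effect of losing patients under item 6.8**

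The documents give no rate of missing covariates, so the rates below are assumptions, applied to the 290 evaluable patients.

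| Assumed loss | Patients lost | n per arm | Power (normal) | Power (t) |
|---|---|---|---|---|
| 0% | 0 | 145 | 83.2% | 82.9% |
| 1% | about 3 | 143.6 | 82.8% | 82.6% |
| 2% | about 6 | 142.1 | 82.4% | 82.2% |
| 5% | about 15 | 137.8 | 81.3% | 81.0% |
| 10% | 29 | 130.5 | 79.1% | 78.8% |

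**Where 80% is crossed**

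n = 2(1.96 + 0.84)² × 13.7²/4.7², which rounds up to 134 per arm, or 268 in total. Power stays at or above 80% until more than 290 − 268 = 22 patients (7.6%) are lost for this reason.

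**The case against.** The strongest reply is that the SAP has already chosen complete cases. The same paragraph of 2.6 restricts each endpoint to patients for whom all relevant data can be calculated, and 6.8 can be read as applying to whatever is still missing after the screening rule. Items 6.1 and 6.2 work in that order for NT-proBNP. Missingness should also be rare: diabetes and permanent AF are strata, and eGFR and ejection fraction are checked for eligibility. A multiple-imputation sensitivity analysis is planned with baseline eGFR, LVEF, diabetes and permanent AF in its model. Finally, *AFib type* may be the field from which permanent AF is derived.

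Much of this stands. The order of rules can be harmonised, but 6.8 does not state it. Complete-case analysis may be what was intended, but that does not make it the better choice when the outcome is observed. The sensitivity analysis does not change the primary analysis. The point about *AFib type* is fair: it should be aligned with the model term, not simply struck out.

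A reader might infer two stronger claims, and the documents support neither.
- *That 6.8 contradicts 2.6 for every covariate.* It does so only for eGFR.
- *That requiring LVEF at randomisation confines the primary analysis to the echo substudy.* That would leave at most 130 of about 320 patients (41%), or 65 per arm, with power near 50%. But SAP 2.3 and 2.6 speak of baseline LVEF, SAP 5.2.2 uses the most recent assessment, and every eligible patient has a qualifying value. The substudy also excludes permanent AF, so this reading would make one of the primary model's own covariates constant. The phrase is loose wording for baseline LVEF.

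**Conclusion.** The point holds in a limited form. Item 6.8 is an operative rule that removes patients with an observed primary outcome for a missing adjustment variable. For eGFR it fails to carry over the SAP's own screening-value rule, and through 2.7 it extends to patients whose only gap is race. A better standard method is available at almost no cost, so the item should be changed.

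The expected size is small. Power falls from about 83% to between 82.8% and 79.1% if 1% to 10% of the evaluable patients are lost. The design suggests that the true rate lies towards the low end, but that is a judgement: the documents give no figure. The calculation uses the plan's difference of 4.7, SD of 13.7 and equal arms, and assumes that the loss is spread evenly between arms.

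**What to change.** Amend SAP 10.2 item 6.8, and 2.6 where needed, before unblinding:

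1. State that 6.8 applies only after the screening-value rule in 2.6, so that a missing randomisation eGFR is taken from screening.
2. Define baseline LVEF as the most recent assessment before randomisation.
3. For any listed covariate still missing, including an eGFR that cannot be calculated because race is missing, fill it by a simple method that ignores arm and outcome, such as the overall mean or mode, or a missing indicator. No patient with an observed 12-week score then leaves the primary analysis because of a covariate named in 6.8. Missing baseline KCCQ is covered separately by item 6.4 and is not affected.
4. Align *AFib type* with the model's permanent-AF term, using the randomisation stratum value if needed.
5. Delete the reference to a first and second primary analysis.

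The choice of filling method matters little, provided that it is fixed in advance. The cost is SAP wording and a few lines of programming; no new data are needed.
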